8.2.2 RELATIONSHIP TO STUDY AGENT

The relationship of LOR to an AE will be determined by the Investigator based on the following definitions:

Not Related

The AE is not related if (1) exposure to LOR or administration of the LOR study injection has not occurred **or** (2) the occurrence of the AE is not reasonably related in time **or** (3) the AE is considered related to another event, medical condition, or product not associated with LOR or the LOR study injection.

Unlikely Related

The AE is unlikely related if (1) the AE is unlikely related in time **or** (2) the AE is considered unlikely to be related to use of LOR or the LOR study injection (i.e., there are no facts [evidence] or arguments to suggest a causal relationship), or the AE is considered possibly related to another event, medical condition, or product not associated with LOR or the LOR study injection.

Possibly Related

The AE is possibly related if (1) LOR or the LOR study injection and AE are considered reasonably related in time **and** (2) the AE could equally be explained by causes other than exposure to LOR or the LOR study injection.

Probably Related

The AE is probably related if (1) LOR or the LOR study injection and AE are considered reasonably related in time **and** (2) LOR or the LOR study injection is more likely than other causes to be responsible for the AE **or** is the most likely cause of the AE.

8.2.3 EXPECTEDNESS

The Sponsor will be responsible for determining whether an AE/SAE is expected or unexpected. An AE/SAE will be considered unexpected if the nature, severity, or frequency of the event is

not consistent with the risk information previously described for the study agent in the IB or is not listed in the IB at the specificity or severity that has been observed.

8.3 TIME PERIOD AND FREQUENCY FOR EVENT ASSESSMENT AND FOLLOW-UP

The reporting period for AEs starts after the Day 1 study injection(s) and ends after the final study visit.

AEs will be followed until the subject's last visit or resolution, whichever comes first. Non-serious AEs that are ongoing at the subject's last visit will be followed for 30 days after their last IA injection or until resolution, whichever comes first. Resolution is defined as the return to baseline status or stabilization of the condition. At the discretion of the Medical Monitor and in consultation with the Investigator, certain non-serious AEs may be followed beyond 30 days. All SAEs will be followed until resolution.

8.4 REPORTING PROCEDURES

8.4.1 ADVERSE EVENT REPORTING

The Investigator is responsible for reporting AEs to the Sponsor via the eCRF and to the IRB according to the protocol and 21 Code of Federal Regulations (CFR) Parts 50, 56, and 312. The Investigator is responsible for ensuring accurate AE information is reviewed and recorded in the subject source and the AE eCRF in a timely manner. The Sponsor is responsible for submitting reports of AEs associated with the use of LOR that are both serious and unexpected to the FDA according to 21 CFR 312.32. All Investigators participating in ongoing studies with LOR will receive copies of these reports from the Sponsor for prompt submission to their IRB/EC according to their institution's requirements.

8.4.2 SERIOUS ADVERSE EVENT REPORTING

The Investigator is responsible for reporting SAEs to the Sponsor and IRB according to 21 CFR Parts 50, 56, and 312.

Using the SAE Report Form, SAEs must be reported within 24 hours of study site personnel's knowledge of the event, regardless of the Investigator assessment of the relationship of the event to study drug. The Investigator should review the SAE information and sign the SAE report, and the Investigator or designee should submit the SAE report to the Sponsor Study SAE email address: [contact] or [contact].

The initial report should include, at a minimum, the following:

- A description of the SAE (including event term and serious criteria)
 - If the subject died, the report should include the cause of death as the event term (with fatal outcome)
- Causal relationship to the study drug
- Subject number, sex, and age
- Details of study drug administration

- The date of the report

Follow-up information must be detailed in a follow-up SAE report and reported to the Sponsor Study SAE email address or fax number as it becomes available. The Investigator also must report all SAEs promptly to the appropriate IRB/EC as required by the institution. Sponsor contact information for questions regarding SAE reporting is provided in [Table 2](#).

Table 2: Sponsor Contact Information for Questions on SAE Reporting

Primary Contact	Alternative Contact
[name], Associate Director, Drug Safety and Pharmacovigilance	[name], Executive Director, Drug Safety and Pharmacovigilance
Cellular: [contact]	
Email: [contact]	Email: [contact]

8.4.3 UNANTICIPATED PROBLEM REPORTING

Incidents or events that meet the criteria for UP (see [Section 8.1.3](#)) require the creation and completion of an UP report. It is the site Investigator's responsibility to report UPs to their IRB and to the Sponsor. The UP report will include the following information:

- Protocol identifying information: protocol title and number, Investigator's name, and the IRB project number;
- A detailed description of the event, incident, experience, or outcome; and
- An explanation of the basis for determining that the event, incident, experience, or outcome represents an UP.

To satisfy the requirement for prompt reporting, UPs will be reported using the following timeline:

- UPs that are SAEs will be reported to the Sponsor and the IRB within 24 hours of the Investigator becoming aware of the event on the SAE report form.
- Any other UP will be reported to the IRB and to the Sponsor within the IRB-required reporting timeframe.

8.4.4 EVENTS OF SPECIAL INTEREST

Not applicable to this study.

8.4.5 REPORTING OF PREGNANCY

If a subject becomes pregnant, the pregnancy is to be followed until the outcome is known. An IRB-approved Pregnant Subject Data Release Form should be completed by the subject in order to obtain consent to follow the progress of the pregnancy and birth, and the health of the infant.

Any subject pregnancy will be collected on a Pregnancy Report Form. Information will be collected for any pregnancy in a female subject which occurs during the study, including

perinatal and neonatal outcome. Infants resulting from such pregnancies should be followed for a minimum of 12 weeks.

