5.3 LIFESTYLE GUIDELINES

5.3.1 CONTRACEPTION

WOMEN OF CHILDBEARING POTENTIAL

Women of childbearing potential (WOCBP) refers to women who are not post-menopausal (defined as 12 months with no menses without an alternative medical cause) or permanently surgically sterile (includes hysterectomy, bilateral salpingectomy, and bilateral oophorectomy).

From the Screening Visit until Month 36 (EOS)/ET, sexually active WOCBP must agree to use an acceptable form of contraception. Acceptable forms of contraception are:

1. Intrauterine device (IUD)
2. Implantable rod
3. Established hormonal contraceptive methods. This includes combined (estrogen and progestogen containing) hormonal contraception associated with inhibition of ovulation (oral, intravaginal, or transdermal); progestogen only hormonal contraception associated with inhibition of ovulation (oral, injectable, or implantable). Females who are using hormonal contraceptives must have had consistent use of the same hormonal contraceptive product for at least 4 weeks.
4. Bilateral tubal ligation/occlusion/division

5. Male partner who had a vasectomy provided that the partner is the sole sexual partner of the WOCBP, and that the vasectomized partner has received medical assessment of the success of the surgical procedure or had the vasectomy for at least 6 months

Sexually active WOCBP who withdraw from the study after receiving study medication should remain on an acceptable form of contraception for 1 month after their last LOR injection.

MEN

For men, no contraception measures are required.

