5.6.2 HANDLING OF PARTICIPANT WITHDRAWALS OR TERMINATION

In case of premature discontinuation of study participation, ET procedures should be conducted within 14 days of discontinuation for any subject who was enrolled in the study, if possible. The date the subject is withdrawn from the study and the reason for the discontinuation should be recorded on the electronic case report form (eCRF). The Investigator or designee must complete all applicable eCRF pages for subjects who discontinue from the study prematurely.

Replacement of subjects who withdraw or discontinue prematurely is not allowed.

Total or Partial Knee Replacement Follow-Up

A subject who has had total or partial knee replacement of the knee diagnosed with OA in unilateral OA or of **both** knees in bilateral OA should be discontinued from the study. In addition to ET procedures as described above, sites should follow up with these subjects approximately 6 months after the total or partial knee replacement surgery as described in [Section 7.1.1](#).

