7. STUDY PROCEDURES AND SCHEDULE

7.1 STUDY PROCEDURES/EVALUATIONS

7.1.1 STUDY SPECIFIC PROCEDURES

Collection of Adverse Events Data

Data regarding AEs will be collected in this study. AEs are events that occur during the study that are not present before the Day 1 study injection(s), or, if present at the time of the Day 1 study injection(s), have worsened in severity during the study. AEs will be assessed at each in-person and phone visit from the time of study injection(s) on Day 1 through Month 36 (EOS)/ET.

Each subject will be observed and queried by the Investigator or designee at each study visit for any continuing AEs or new AEs since the previous visit. The subject may be asked to return to the site for an unscheduled visit if an AE occurs between study visits, and if, in the opinion of the Investigator, the AE requires a study visit for full evaluation. The following information will be recorded within the eCRF for each AE: Description of the event, date of onset and resolution, etiology, and severity as assessed by the Investigator according to the Clinical Data Interchange Standards Consortium (CDISC) Severity/Intensity Scale for Adverse Events (AESEV) ([Table 1](#)), causal relationship to LOR or LOR injection, outcome, and any action taken.

In this protocol, signs and symptoms of exacerbation or worsening of knee OA will be captured in the context of efficacy assessments and recorded on specific pages of the eCRF. Anticipated fluctuations or anticipated deterioration (in the opinion of the Investigator) of the underlying disease (knee OA) will not be considered as AEs nor captured on the AE page of the eCRF.

Whenever possible, it is preferable to record a diagnosis as the AE term rather than a series of symptoms relating to a diagnosis. Fluctuations of pre-existing conditions that do not represent a clinically significant exacerbation or worsening need not be considered AEs.

AEs will be followed until the subject's last visit or resolution, whichever comes first. Non-

serious AEs that are ongoing at the subject's last visit will be followed for 30 days after their last study injection or until resolution, whichever comes first. Resolution is defined as the return to baseline status or stabilization of the condition. At the discretion of the Medical Monitor and in consultation with the Investigator, certain non-serious AEs may be followed beyond 30 days. All SAEs will be followed until resolution.

Medical History

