4. OVERALL STUDY DESIGN AND PLAN

This study was a multicenter and open-label study evaluating the real-world use of 0.07 mg lorecivint (LOR) injected into one or both knee joints of subjects with OA at Day 1. Additional injections were to be performed per the OA treatment algorithm available in the study protocol.

The sponsor elected to terminate this study early for business reasons. All active subjects were requested to complete an early termination (ET) visit. Subjects who were recently injected were requested to participate in an ET visit 30 days (+14 days) after their last injection. Subjects on study more than 30 days since their last injection, were requested to participate in an ET visit as soon as possible. During the ET visit, only safety data were to be collected.

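### When a subject withdraws soon after a LOR injection, collection of new AEs ends at the ET visit, which can fall before the post-injection month is over, and pregnancy collection in that month is unclear

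*Protocol*

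**What the plan says.** **New AEs.** Protocol section 8.3: "The reporting period for AEs starts after the Day 1 study injection(s) and ends after the final study visit". Section 7.1.1 agrees: "AEs will be assessed at each in-person and phone visit from the time of study injection(s) on Day 1 through Month 36 (EOS)/ET".

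**AEs already ongoing.** Section 8.3 says that non-serious AEs still open at the last visit "will be followed for 30 days after their last IA injection or until resolution, whichever comes first". Section 7.1.1 has the same rule but counts from the last study injection. SAEs are followed to resolution.

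**Timing of ET.** Section 5.6.2: "ET procedures should be conducted within 14 days of discontinuation for any subject who was enrolled in the study". The sentence goes on to qualify this as something to do where possible, and section 7.3.6 has the same qualifier. Neither section refers to the date of the last injection.

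**Contraception.** Under section 5.3.1, sexually active women of childbearing potential who withdraw after study medication "should remain on an acceptable form of contraception for 1 month after their last LOR injection".

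**Pregnancy.** Section 8.4.5 contains both "Any subject pregnancy will be collected on a Pregnancy Report Form" and, directly after it, "Information will be collected for any pregnancy in a female subject which occurs during the study". The last pregnancy test is the urine test at Month 36 or ET (section 7.2.2).

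**Sponsor termination.** SAP section 4 (Overall Study Design and Plan): "Subjects who were recently injected were requested to participate in an ET visit 30 days (+14 days) after their last injection". SAP section 5.1.2 repeats this.

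**The concern.** The protocol uses a period of about a month after an injection twice: 30 days for following ongoing non-serious AEs, and 1 month for contraception after withdrawal. Neither period governs when collection of new events stops. In an individual withdrawal that point is the ET visit, and the ET visit is tied to the decision to leave.

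A subject who leaves a few days after LOR may therefore have no planned contact for most of the month that follows. The 4-week safety call is scheduled only after the Day 1 injection (sections 4.1 and 7.3.3), so after a later LOR injection the ET visit may be the only remaining contact. Section 2.3.1 names infection and local reactions as risks of knee injection, and safety and tolerability is the primary objective. A new event of this kind after ET would be outside the stated period and nobody would ask about it.

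For pregnancy, withdrawing women are asked to take a precaution for a month in which the plan does not say clearly whether a pregnancy is recorded.

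**Working it through.** The plan gives no figure for this point, so there is none to reproduce. The check is day arithmetic.

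**Inputs**
- Post-injection month: 30 days (sections 7.1.1 and 8.3; the 1 month in section 5.3.1 is assumed to be 30 days).
- ET: 0 to 14 days after withdrawal (section 5.6.2, a target and not a hard limit).
- Last permitted LOR injection: Month 33 (section 4.1.1).
- Scheduled final visit: Day 1080 ± 28 (section 7.3.5).
- ET at sponsor termination: 30 to 44 days after the last injection for the recently injected (SAP section 4).

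**1. Individual withdrawal.** If withdrawal is on day d after LOR, ET falls between d and d + 14. Days of the month left after ET = max(0, 30 − ET day).

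| Withdrawal day d | ET day | Days left after ET |
|---|---|---|
| 0 | 0 to 14 | 30 to 16 |
| 7 | 7 to 21 | 23 to 9 |
| 14 | 14 to 28 | 16 to 2 |
| 21 | 21 to 35 | 9 to 0 |
| 30 | 30 to 44 | 0 |

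Even with ET at the 14-day target, collection closes before Day 30 if d + 14 < 30, that is, d < 16. Reading a month as 28 or 31 days moves the maximum to 28 or 31.

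**2. Scheduled final visit.** On the protocol's 30-day months, Month 33 is Day 33 × 30 = 990. The earliest Month 36 visit is Day 1080 − 28 = 1052. The gap is 1052 − 990 = 62 days. In calendar months, Month 33 is about Day 1004 and the gap is 1052 − 1004 = 48 days. Both exceed 30, so no days are left uncovered.

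**3. Sponsor termination.** With ET at 30 to 44 days, no days are left uncovered.

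**4. How many subjects.** The documents give no withdrawal rate or timing, so this is illustrative. Assume that 15% to 45% of 300 withdraw (45 to 135), that timing is unrelated to injection, that follow-up is 1080 days, and that there are 1 to 6 LOR dates per subject. Six is the most for one knee at 6-month spacing up to Month 33.

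Affected = withdrawals × (exposed days per LOR date × LOR dates) / 1080.
- ET on the day of withdrawal (30 exposed days): 45 × 30/1080 = 1.25; 135 × 180/1080 = 22.5.
- ET 14 days later (16 exposed days): 45 × 16/1080 = 0.67; 135 × 96/1080 = 12.0.

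If the two knees are injected on different dates there can be more than six LOR dates, which raises the upper end. So would withdrawal that clusters after a poorly tolerated injection. The share of women of childbearing potential is not given, so no pregnancy count is possible.

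**The case against.** The best case against the point is that little is lost. A subject who leaves because an injection was badly tolerated will usually have that AE already. It is recorded at ET and then followed, so only a further, new event is missed. The SAE reporting rule in section 8.4.2 runs from site knowledge and states no end date. The 14 days is a target, so some ET visits will be later. In the study as it ended, SAP section 8.1 reports only 2 AEs and plans no AE tables, so there is no incidence table to distort. All of this stands, and it keeps the point small. It does not remove the gap, because none of these provisions asks about a new non-serious event after ET.

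A reader might infer more than the documents support:
- **That the Month 36 visit has the same problem.** It does not; the gap to the last permitted LOR injection is at least 48 days.
- **That pregnancy reporting closes at ET.** Section 8.4.5 never names ET as a cut-off, and "Any subject pregnancy will be collected on a Pregnancy Report Form" has no time limit. The wording is ambiguous; it does not exclude these pregnancies.
- **That harms in this month go unreported.** Known SAEs are reportable and ongoing AEs are followed. The defect is that new events are not solicited and lie outside the stated period.
- **That section 5.3.1 defines a risk month for AEs.** It concerns contraception only. For AEs, the internal comparison is the 30-day follow-up in sections 7.1.1 and 8.3.
- **That AE incidence is biased downward.** This is possible, but nothing in the documents shows it.

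**Conclusion.** The point holds for one group: subjects who withdraw individually within about a month of a LOR injection. For them, up to 30 days after the injection can pass with new AEs neither solicited nor inside the reporting period. With ET at the 14-day target, the maximum is 16 days. Separately, the plan is ambiguous on whether a pregnancy in the contraception month is collected, and no test is scheduled after ET. Subjects who reach Month 36 are not affected. Recently injected subjects still active at sponsor termination were covered if they attended as requested.

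The number affected cannot be derived from the documents. The range of about 0.7 to 23 subjects rests entirely on the assumed withdrawal rate, the assumed number of LOR dates, and timing unrelated to injection. This is an inexpensive improvement to safety capture and does not invalidate any planned analysis.

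**What to change.** Reconcile Protocol sections 5.3.1, 5.6.2, 7.1.1, 8.3 and 8.4.5 with each other. State one closing point for collecting new AEs and one for pregnancies, each set no earlier than the post-injection period that the protocol already uses for that purpose. Resolve the two sentences in section 8.4.5, and use the same injection reference in sections 7.1.1 and 8.3. Which contraception period is right is not a matter for this review.

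Where ET falls before the closing point and the subject agrees, add one safety phone contact in the existing Month 1 phone-visit format. The sponsor's request at termination for ET at 30 (+14) days suggests that timing a last contact from the injection was considered workable.

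No extra SAP sentence is needed, because SAP section 8.1 already treats all collected AEs as treatment emergent. For the study as terminated, adding days from last LOR injection to last contact to the exposure listing in SAP section 9.2 would show whether any early withdrawer was affected.

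The cost is a few sentences and a few calls. Subjects who refuse contact will still be missing.

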8.5 STUDY HALTING RULES

Not applicable to this study.

8.6 SAFETY OVERSIGHT

Clinical safety oversight will be performed by centralized review conducted by Medical Monitors per the Medical Monitoring Plan. In addition, appropriate monitoring will be conducted by Clinical Research Associates.

9. CLINICAL MONITORING

All aspects of the study will be monitored by the Sponsor or the Sponsor's designees with respect to current GCP and Standard Operating Procedures (SOPs) for compliance with applicable government regulations. It is the responsibility of the Investigator to provide all study records, including eCRFs and source documents among other records, for review and inspection by the clinical monitor.

Clinical monitoring will be performed per the Clinical Monitoring Plan. Clinical monitors will periodically evaluate the progress of the study, including the verification of appropriate consent form procedures and the verification of the accuracy and completeness of eCRFs. Clinical monitors will also ensure that all protocol requirements, applicable US FDA regulations, other regulatory requirements, and the Investigator's obligations are being fulfilled.

Centralized data monitoring will be performed per the Centralized Data Monitoring Plan in order to periodically evaluate study progress and risks. A regular report of risks will be utilized together with centralized data monitoring to direct overall monitoring focus and activities to the areas of greatest risk which have the most potential to impact subject safety and data quality.

The accuracy of the data will be verified by reviewing the documents described in [Section 11](#).

10. STATISTICAL CONSIDERATIONS

10.1 STATISTICAL AND ANALYTICAL PLANS

This section describes the planned statistical analyses in general terms. A complete description of the statistical analyses will be specified in a statistical analysis plan (SAP), finalized prior to database lock.

10.2 STATISTICAL HYPOTHESES

No formal hypotheses are being tested in this study.

10.3 ANALYSIS DATASETS

Full Analysis Set (FAS): All subjects who receive a study injection.

Safety Analysis Set (SAS): All subjects who receive a study injection. In this study, FAS and SAS will be identical.

Additional analysis sets may be defined and included in the SAP.

10.4 DESCRIPTION OF STATISTICAL METHODS

10.4.1 GENERAL APPROACH

For continuous variables, the number of subjects in the analysis, mean, standard deviation (SD), median, minimum, and maximum will be reported. All categorical endpoints will be summarized using frequencies and percentages.

